16. PHARMACODYNAMIC ANALYSIS

16.1. PHARMACODYNAMIC ASSESSMENTS

The pharmacodynamics of KA34 will be evaluated by examining several exploratory endpoints, including biomarker data from serum levels of the N-propeptide of type IIA collagen (PIIANP) and urinary excretion of C-terminal cross-linking telopeptide of type II collagen (CTX-II).

Clinical symptoms as assessed by the Western Ontario and McMaster Universities Osteoarthritis Index (WOMAC) Version 3.1 total score and the WOMAC pain and function subscale scores, and Tibial-femoral radiographs imaging data are exploratory, see Section 18.

The pre-treatment values for PIIANP and CTX-II endpoints will be compared to post-treatment measurements and both the absolute and percent change from baseline will be summarized. Descriptive statistics for PD endpoints by time point and by dose levels. An exploratory analysis of PK/PD endpoints may also be performed but is not planned.

A listing of PD sample collection times and subject listings of all PIIANP and CTX-II concentration-time data for each dose levels will be presented. Summary tables for both the observed values and the baseline-corrected values. Figures of mean baseline-corrected concentration-time data will be presented by each dose levels. Individual observed concentration-time data for each subject will be presented graphically.

16.2. PHARMACODYNAMIC PARAMETERS

Not applicable to this study.

16.3. PHARMACOKINETIC-PHARMACODYNAMIC RELATIONSHIPS

Not applicable to this study.

17. SAFETY OUTCOMES

All outputs for safety outcomes will be based on the Safety Analysis Set.

There will be no statistical comparisons between the dose levels for safety data, unless otherwise specified with the relevant section.

Document: CALIBR_CBR-KA34-3001_SAP_Final 1.0
Author: PPD Version Number: Final 1.0
Version Date: 15MAY2020

Template No: CC Effective Date: 01Apr2016

17.1. ADVERSE EVENTS

Adverse Events (AEs) will be coded using MedDRA central coding dictionary, Version 21.0.

Treatment emergent adverse events (TEAEs) are defined as AEs that started on or after the first dose of study medication.

Pretreatment AEs are defined as AEs occurring prior to dosing. These events will be presented in the listings only and are not included in the tabular summary of AEs.

See APPENDIX 2 for handling of partial dates for AEs. In the rare case where it is not possible to assess treatment emergence, the AE will be classified as treatment emergent (i.e. the worst case).

Severity

AE Severity is classified as mild/moderate/severe. If a subject reports a TEAE more than once within that SOC/ PT, the AE with the worst case severity will be used in the corresponding severity summaries.

Relationship to Study Medication

Relationship to study medication, as indicated by the Investigator, is classified as "not related", "unlikely related", "possibly related", or "related". A "related" TEAE is defined as a TEAE with a relationship to study medication as "possibly related" or "related" to study medication. TEAEs with a missing relationship to study medication will be regarded as "related" to study medication. If a subject reports the same AE more than once within that SOC/ PT, the AE with the worst case relationship to study medication will be used in the corresponding relationship summaries.

All AE tabulations will be performed for the SAD and MAD study part by dose levels and for all active treated subjects overall, and will include the number and percentage of subjects. Incidence of TEAEs will be tabulated by the following:

- Overall summary for TEAEs displaying number (percent) of subjects with at least one TEAE, with at least one related TEAE, with at least one severe TEAE, with at least one severe related TEAE, with at least one serious AE, with TEAEs leading to discontinuation and with TEAEs leading to death
- Summary of TEAEs by SOC and PT
- Summary of Treatment-related AEs by SOC and PT
- Summary of TEAEs by SOC, PT and Severity
- Summary of Treatment-related AEs by SOC, PT and Severity
- Summary of Serious TEAEs by SOC, PT and Severity

Document: CALIBR_CBR-KA34-3001_SAP_Final 1.0
Author: PPD Version Number: Final 1.0
Version Date: 15MAY2020

Template No: C Reference: Reference: C

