| ALLOWABLE VISIT WINDOW           | -28 to -1 days |                           |     | -/- 2     | +/ <del>-</del>       | -/-       | -/+       | -/+      | -/+      |                       | -
1                | + 1                               | - <del>-</del>              | +/-       | + %                    | -/+   | 30                        |
|                                  | ,              |                           |     | Min       | Min                   | Min       | Min       | Min      | Min      |                       | Day L I    | Day L Day L | $\mathrm{Day}^{\mathrm{L}}$ | Day       | Days                   | Days  | Days                      |
| Adverse Events H      |                |                           | X   | X         | X                     | X         | X         | X        | ×        | X                     | X                     | X                                 | ×                           | X         | X                      | ×   | X                         |
| Contraception Review             | X              |                           |     |           |                       |           |           |          | X        | X                     | X                     | X                                 | X                           | X         |                        |   |                           |

A Day 2 and Day 50 Visits may be conducted via telephone

B Vital signs (temperature, seated blood pressure, and pulse rate) should be collected pre-dose and 30 minutes after dosing on Days 8, 15, and 22

C Tibial-femoral x-rays to confirm the diagnosis of OA and Kellgren & Lawrence Grade must be of acceptable quality and acquired within 6 months prior to Screening

D Safety laboratory testing includes hematology, chemistry, and urinalysis; will be performed at the site's laboratory

E For female subjects; will be performed at the site's laboratory

F The WOMAC should be administered at the beginning of the visit prior to completing other procedures

G Optional banked biospecimen collection

H Adverse Events are captured starting at time of consent. Any Adverse Events during Screening and Day 1 will be captured and noted as part of medical history

Screening procedures may be completed across multiple days during the 28 day screening period and do not need to be conducted on consecutive days

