#### 8.2. Definitions

#### 8.2.1. Adverse Events

An AE is any untoward medical occurrence in a study subject administered a product or medical device; the event need not necessarily have a causal relationship with the treatment or usage to be considered an AE. Examples of AEs include, but are not limited to:

- Abnormal test findings
- Clinically significant signs and symptoms
- Changes in physical examination findings
- Hypersensitivity
- Progression/worsening of underlying disease
- Drug abuse
- Drug dependency

Additionally, AEs may include signs and symptoms resulting from:

- Drug overdose
- Drug withdrawal

- Drug misuse
- Drug interactions
- Extravasation
- Exposure during pregnancy
- Exposure via breastfeeding
- Medication error
- Occupational exposure

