### 8.3. Severity Assessment

| If required on the AE page of the CRF, the investigator will use the adjectives MILD, MODERATE, or SEVERE to describe the maximum intensity of the AE. For purposes of consistency, these intensity grades are defined as follows: |   |  |
|--|---|--|
| MILD   | Does not interfere with subject's usual function        |  |
| MODERATE   | Interferes to some extent with subject's usual function |  |
| SEVERE   | Interferes significantly with subject's usual function  |  |

Note the distinction between the severity and the seriousness of an AE. A severe event is not necessarily an SAE. For example, a headache may be severe (interferes significantly with the subject's usual function), but would not be classified as serious unless it met one of the criteria for SAEs listed above.

The AEs may also be graded with the Common Terminology Criteria for Adverse Events (CTCAE) version 5.

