2. STUDY OBJECTIVES

2.1. **PRIMARY OBJECTIVE**

To assess the safety and tolerability of KA34 when administered via intra-articular injection to the knee joint

2.1.1. **PRIMARY ENDPOINTS**

Incidence, relatedness, severity, and duration of treatment emergent adverse events (TEAEs)

2.2. **SECONDARY OBJECTIVES**

- To identify any dose limiting toxicity and determine the maximum tolerated dose of KA34
- To determine pharmacokinetic properties of KA34 in plasma

2.2.1. **SECONDARY ENDPOINTS**

- Changes from baseline in clinical laboratory test results, vital signs, or electrocardiogram (ECG) results
- Clinically significant findings on physical examination
- Pharmacokinetic parameters of KA34 in plasma including:
 - Maximum observed plasma concentration (C_{max})
 - Dose-adjusted C_{max} (C_{max}/dose)
 - Time to maximum observed plasma concentration (T_{max})

Document: CALIBR CBR-KA34-3001 SAP Final 1.0 Author: Version Number: Final 1.0 PPD Version Date: 15MAY2020 Template No: CC

Effective Date: 01Apr2016

- Area under the plasma concentration vs. time curve from time zero to the last quantifiable concentration (AUC_{0-t})
- Dose-adjusted AUC_{0-t} (AUC_{0-t}/dose)
- AUC from time zero to infinity (AUC_{0-inf})
- Dose-adjusted AUC_{0-inf} (AUC_{0-inf} /dose)
- Terminal elimination rate constant (λz)
- Terminal half-life (t_{1/2})
- Apparent clearance (CL/F)
- Volume of distribution (Vz/F)

2.3. **EXPLORATORY OBJECTIVES**

- To assess changes in cartilage and osteoarthritis (OA) symptoms after administration of KA34
- To collect and bank biospecimen samples for exploratory biomarker research

2.3.1. **EXPLORATORY ENDPOINTS**

- Serum levels of the N-propeptide of type IIA collagen (PIIANP) as a pharmacodynamic marker of collagen synthesis
- Urinary excretion of C-terminal cross-linking telopeptide of type II collagen (CTX-II) as a pharmacodynamic marker of collagen degradation
- Change from baseline in Whole-Organ Magnetic Resonance Imaging Score (WORMS) of the index knee
- Change from baseline of the Western Ontario and McMaster Universities Osteoarthritis Index (WOMAC) Version 3.1 total score and the WOMAC pain and function subscale scores
- Utilize banked biospecimen samples for exploratory research related to drug response in OA

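### The TEAE definition has no worsening clause, so whether a pre-dose AE that worsens after injection reaches the primary-endpoint tables depends on how the site records it

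*SAP*

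**What the plan says.** The primary endpoint is the incidence, relatedness, severity and duration of TEAEs (protocol 2.2, SAP 2.1.1). The protocol uses the term TEAE without defining it, so the working definition is the one in SAP 17.1: "Treatment emergent adverse events (TEAEs) are defined as AEs that started on or after the first dose of study medication". The same section adds "Pretreatment AEs are defined as AEs occurring prior to dosing", and of those events it says "These events will be presented in the listings only and are not included in the tabular summary of AEs". Its one safeguard is a worst-case rule: "In the rare case where it is not possible to assess treatment emergence, the AE will be classified as treatment emergent".

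On recording, protocol 8.3 asks the investigator to choose mild, moderate or severe "to describe the maximum intensity of the AE", which gives one value per event. Protocol 8.2.1 lists "Progression/worsening of underlying disease" among its examples of AEs, and 5.4 requires every post-injection flare to be reported as an AE.

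The passages differ on when recording starts. Footnote H of both schedules begins "Adverse Events are captured starting at time of consent", then says that AEs in Screening and on Day 1 are noted as medical history. Protocol 8.1 starts AE collection at first administration on Day 1. Sections 6.2.1 and 6.3.1 assess AEs from the time of administration.

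**The concern.** A definition based on start date handles new events well but says nothing about an event already present at dosing that gets worse. Screening lasts up to 28 days, so an event can begin in that period and still be ongoing at injection. If it then goes from mild to severe and the site updates the existing record, the database holds one AE with a pre-dose start and a severity of severe. The SAP classes that record as pretreatment and does not tabulate it.

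The primary-endpoint tables are at stake: any TEAE, severe TEAE, related TEAE and the breakdowns by system organ class and preferred term. The table of TEAEs of CTCAE grade 3 or higher (SAP 17.1.3) uses the same definition. The error can only lower the counts. With about 4 sites and no recording rule, differences between dose levels could partly reflect site habit.

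**Working it through.** No figure in the plan can be reproduced here, because safety has no power, alpha or expected event rate. The check is a reading of the rules case by case, plus one division.

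**Step 1. Apply the definition to each way an event can be recorded.**

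| Situation | Governing text | Result |
|---|---|---|
| Flare after injection | Protocol 5.4: reported as an AE; it starts after dosing | TEAE |
| Worsening of the knee osteoarthritis | Protocol 8.2.1: the worsening is itself an AE | TEAE if entered with a post-dose start |
| Condition held only in medical history that worsens | No earlier AE record exists to update | TEAE if the worsening is entered as an AE with a post-dose start |
| AE recorded before dosing that worsens; site opens a second record | SAP 17.1: second record starts after dosing | TEAE |
| AE recorded before dosing that worsens; site updates the one record | Protocol 8.3 keeps the maximum intensity; start date stays pre-dose | Pretreatment, listings only |
| Emergence cannot be assessed | SAP 17.1 worst-case rule | TEAE |

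The fourth and fifth rows describe the same clinical course with different results, and no passage says which way to record it.

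**Step 2. Check whether another rule rescues the fifth row.** The worst-case rule does not, because a known pre-dose start date allows emergence to be assessed. The rule that takes the worst severity within a preferred term does not either, because the severity summaries use only records already classed as TEAEs.

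**Step 3. Check whether pre-dose AE records can exist.** Footnote H sends Screening events to medical history and protocol 8.1 starts collection at first dose, so few are expected. However, SAP 17.1 defines pretreatment AEs and plans to list them, so the analysis plan allows for such records.

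**Step 4. Size for one affected subject.** The tables count subjects with at least one event. If the subject has no other event in that row, the shift is 100 × 1/n percentage points, where n is the number of active subjects (SAP 3.1).

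| Cohort | n | Shift |
|---|---|---|
| Single dose, 50 and 100 µg | 3 | 1/3 = 33.3 |
| Single dose, 200 and 400 µg | 6 | 1/6 = 16.7 |
| Multiple dose, each level | 9 | 1/9 = 11.1 |

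If the subject already has another TEAE in the row, the shift is 0. The values in the table are therefore upper limits per subject and do not apply to every omitted event.

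**The case against.** The strongest reply is that the protocol already directs the important cases elsewhere. Every subject enters with index-knee pain of at least 40 mm on the VAS, and a reader might infer that aggravation of that pain is what the definition drops. The documents do not support this. Baseline knee pain is an entry criterion, and osteoarthritis symptoms are taken as history at Screening (protocol 6.1), so they are not a pre-dose AE. Worsening of the underlying disease is an AE under 8.2.1, and flare must be reported under 5.4. Either counts once entered with a post-dose start. This part of the reply stands.

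A reader might also infer that every event that worsens after dosing is lost. That too goes beyond the text: the loss occurs only when the worsening stays on a record with a pre-dose start.

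It is also fair to say that the information is not hidden. Pretreatment AEs appear in listings, and SAP 17.1.2 lists serious events without an emergence condition. SAP 4.1 places DSMB reporting outside the SAP, and protocol 3.2 bases escalation review on adverse events generally. Escalation is not affected.

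The reply does not close the gap in the fifth row of the table. The SAP provides for pretreatment AE records, and no passage gives a new-record rule for them.

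**Conclusion.** The gap is real but narrow. An AE entered before dosing that worsens after injection is left out of the TEAE, severe TEAE and related TEAE tables if the site keeps it as one record, and included if the site opens a second. It mainly concerns events other than flare and worsening of the osteoarthritis, and it touches only the final tables.

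The documents give no rate for such events, so no expected count can be stated. The per-subject limits are 33, 17 and 11 percentage points, and they assume the planned cohort sizes and no other event in the row.

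Two uncertainties remain. The text of SAP Appendix 2, which contains an algorithm for treatment emergence, was not available for this check; SAP 17.1 refers to it only for partial dates. Footnote H may mean only the pre-dose part of Day 1, but it does not say so. Taken literally it conflicts with protocol 8.1 and SAP 17.1 for an event a few hours after the first injection, which is when 5.4 expects flare.

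The change should be made, because the definition governs the primary endpoint and the remedy is cheap.

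**What to change.** 1. In SAP 17.1, define a TEAE as an AE that starts on or after the first dose, or that starts before it and increases in severity or becomes serious on or after it. Confirm that the Appendix 2 algorithm agrees.
2. Add a CRF completion instruction, reflected in protocol 8.1, that post-dose worsening of a pre-dose AE or a medical-history condition is entered as a new AE dated to the worsening. The clause needs this, because a single record with one start date and one maximum intensity does not show when the severity changed.
3. Reconcile footnote H in both schedules with protocol 8.1 and SAP 17.1, so that the status of Day 1 events after dosing is the same throughout.

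The cost is SAP wording, one programming rule, one site instruction and a corrected footnote. It is best done before database lock and unblinding. The downside is a slightly higher TEAE count.

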17.1.1. TEAEs Leading to Discontinuation of Study Medication

TEAEs leading to permanent discontinuation of study medication will be identified by using the variable pertaining to action taken field on the Adverse Events page of the electronic case report form ((e)CRF), and listed.

17.1.2. SERIOUS ADVERSE EVENTS

Serious adverse events (SAEs) are those events recorded as "Serious" on the Adverse Events page of the (e)CRF, and will be listed.

17.1.3. CTC GRADING FOR ADVERSE EVENTS

AEs will be graded by the clinics using the Common Terminology Criteria for Adverse Events (CTCAE) version 5 grading system. A summary table will be presented for TEAEs with CTCAE grade >=3 by SOC and PT.

17.2. DEATHS

If any subjects die during the study as recorded on the adverse events page of the (e)CRF, the information will be presented in a data listing.

17.3. LABORATORY EVALUATIONS

Laboratory results will be included in the reporting of this study for Hematology, Blood Chemistry and Urinalysis. A list of laboratory assessments to be included in the outputs is included in the protocol, Section 7.1.1. Presentations will use SI Units, as provided by the labs.

Protocol-specified clinical laboratory tests will be summarized using descriptive statistics for the SAD and MAD parts. Clinical laboratory data collected during study conduct, which were not required per protocol, such as for special testing to evaluate an AE, will be listed separately and not summarized.

Quantitative laboratory measurements reported as "< X", i.e. below the lower limit of quantification (BLQ), or "> X", i.e. above the upper limit of quantification (ULQ), will be converted to X for the purpose of quantitative summaries, but will be presented as recorded, i.e. as "< X" or "> X" in the listings.

The following summaries will be provided for laboratory data:

 Actual, change from baseline and percentage change from baseline by dose levels and visit (for quantitative measurements)

Document: CALIBR_CBR-KA34-3001_SAP_Final 1.0
Author: PPD Version Number: Final 1.0
Version Date: 15MAY2020

Template No: Fefective Date: 01Apr2016

Copyright © 2017 IQVIA. All Rights Reserved.

- Shift from baseline according to normal range criteria (for quantitative measurements and categorical measurements) for all on-treatment assessments.
- Listing of lab results outside the normal range

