J All D1 predose laboratory assessments should be conducted within 48 hours prior to IP administration and other pre-dose assessments conducted within 2 hours prior to IP administration

K Subjects may be discharged after at least 2 hours of safety observation following the last procedure

L There should be minimum of 7 days between the IA injections

M Procedures may be split into 2 days to allow for the completion of multiple procedures

N Assessments that do not require a visit such as review of concomitant medications for Day 180 may be done remotely via phone call, text message, email. PE can be conducted by telemedicine. Laboratory assessment can be done at laboratories other the clinical sites

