#### 3. STUDY DESIGN

#### 3.1. Study Overview

This is a randomized, double-blind, placebo-controlled study to assess the safety, tolerability, pharmacokinetics, and pharmacodynamics of KA34 when administered via intra-articular injection to subjects with osteoarthritis of the knee. All subjects will receive a 5 mL injection of KA34 or placebo in the affected knee.

The study will consist of approximately 7 cohorts of subjects who will be randomized to receive KA34 or placebo. KA34 will be provided as a solution with a concentration of 200 µg per mL.

KA34 will be administered as a single dose to the following cohorts:

| DOSE            | N PER COHORT               |
|-----------------|----------------------------|
| 50 μg per knee  | 4 (3 – Active & 1 Placebo) |
| 100 μg per knee | 4 (3 – Active & 1 Placebo) |
| 200 μg per knee | 8 (6 – Active & 2 Placebo) |
| 400 μg per knee | 8 (6 – Active & 2 Placebo) |

Once the safety and tolerability of single doses of KA34 have been assessed, multiple-dose administration of KA34 will be evaluated. The multiple-dose portion of the study will be initiated after a thorough review of the safety data from the single-dose cohorts. During the multiple dose portion of the study, KA34 will be administered as 4 weekly doses to the following cohorts:

| DOSE                          | N PER COHORT                |
|-------------------------------|-----------------------------|
| 100 μg per knee per injection | 12 (9 – Active & 3 Placebo) |
| 200 μg per knee per injection | 12 (9 – Active & 3 Placebo) |
| 400 μg per knee per injection | 12 (9 – Active & 3 Placebo) |

The doses administered to subsequent cohorts in either the single or multiple dose portions of the study may be lowered if any safety or tolerability issues are identified which suggest that the planned doses may pose a risk to study participants. Additional dose groups may be added to the study depending on the observed safety and tolerability profile of KA34 or if the pharmacokinetic data permit a higher than anticipated dose while remaining within a safe exposure limit based on the toxicokinetics and safety profile from the nonclinical toxicology studies.

The study will be conducted at approximately 4 sites in the United States. Approximately 60 subjects will be randomized to participate in this trial.

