# **7.1. Safety**

# 7.1.1. Laboratory Tests

The following safety laboratory tests will be performed as defined in the Schedule of Activities and Study Procedures section of this protocol at the site local laboratory:

 Table 1
 Laboratory Tests

| Hematology – Complete Blood Count   |   |  |
|---|---|--|
| 
 
Red Blood Cell (RBC) Count
 
Hemoglobin (Hb)
 
Hematocrit (Hct)
 
Mean Corpuscular Volume (MCV)
 
Mean Corpuscular Hemoglobin (MCH)
 
Mean Corpuscular Hemoglobin Concentration (MCHC)
 
Platelet Count (Plt)
 
 | 
 
White Blood Cell (WBC) Count
 
Absolute Neutrophil Count
 
Absolute Lymphocyte Count
 
Absolute Monocyte Count
 
Absolute Eosinophil Count
 
Absolute Basophil Count
 
 |  |
| Chemistry – Metabolic Panel   |   |  |
| 
 
Glucose
 
Calcium
 
Albumin
 
Total Protein
 
Sodium
 
Potassium
 
Bicarbonate (Total CO2)
 
Chloride
 
   | 
 
Blood Urea Nitrogen (BUN)
 
Creatinine
 
Alkaline Phosphatase (ALP)
 
Alanine Aminotransferase (ALT)
 
Aspartate Aminotransferase (AST)
 
Total Bilirubin
 
            |  |
| Urina   | lysis   |  |
| 
 
Specific Gravity
 
pH
 
Protein
 
Glucose
 
Ketones
 
Blood (Hemoglobin)
 
Leukocyte Esterase
 
   | 
 
Nitrite
 
Bilirubin
 
Urobilinogen
 
Microscopic ExaminationA
 
   |  |
| Other Labor   | atory Tests   |  |
| 
 
Follicle-Stimulating Hormone (FSH)B
 
Urine Drug Screen
 
   |   |  |

A Only if urine dipstick is positive for blood, protein, nitrites or leukocyte esterase

B For female subjects

The minimum requirement for urine drug screening includes cocaine, opiates/opioids, benzodiazepines, and amphetamine.

Urine drug screening conducted during Screening in the SAD and MAD part of the study must be negative for subjects to receive investigational product.

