# 8.4. Special Situations

# 8.4.1. Potential Cases of Drug-Induced Liver Injury

Potential cases of drug-induced liver injury (DILI) are to be reported as SAEs, irrespective of availability of all the results of the investigations performed to determine etiology of the liver function test abnormalities.

A potential DILI or Hy's law case is considered a confirmed case after the results of reasonable investigations have been received and an alternative etiology has been excluded.

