17.3.1. LABORATORY REFERENCE RANGES

Quantitative laboratory measurements will be compared with the relevant laboratory reference ranges by the lab vendors and categorized as:

- Low: Below the lower limit of the laboratory reference range.
- Normal: Within the laboratory reference range (upper and lower limit included).
- High: Above the upper limit of the laboratory reference range.

Clinical laboratory reference/normal ranges will be listed.

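### SAP 17.3 has no rule for multiple-dose Day 180 laboratory results that come from a different laboratory than baseline, and no laboratory table grades liver results above High by dose

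*SAP*

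**What the plan says.** **Where tests are run.** Protocol 7.1.1 places safety tests at the site's own laboratory; its wording ends "section of this protocol at the site local laboratory". Protocol 3.1 says "The study will be conducted at approximately 4 sites in the United States". For Day 180 in the multiple-dose cohorts only, footnote N of the schedule adds "Laboratory assessment can be done at laboratories other the clinical sites", and Protocol 6.3.9 repeats the permission.

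**What is tabulated.** SAP section 1 states that it rests on Amendment 4 (02 April 2020), so the permission was known. SAP 17.3 plans "Actual, change from baseline and percentage change from baseline by dose levels and visit (for quantitative measurements". On units it says "Presentations will use SI Units, as provided by the labs". SAP 6.5 takes the latest available scheduled pre-dose value as baseline and sets no condition on the laboratory. Change from baseline in laboratory tests is a secondary endpoint (Protocol 2.4, SAP 2.2.1).

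**Use of reference ranges.** SAP 17.3.1 classes each quantitative result as Low, Normal or High against the relevant laboratory's range. SAP 17.3 tabulates shifts in that class, limited to on-treatment assessments (not defined), and lists out-of-range results. SAP 17.3.1 adds "Clinical laboratory reference/normal ranges will be listed".

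**Liver.** Protocol 7.1.1 (Table 2) lists extra tests for suspected liver injury, and 8.4.1 says "A potential DILI or Hy's law case is considered a confirmed case after the results of reasonable investigations have been received". Neither document states a threshold in multiples of the upper limit of normal (ULN), and the SAP plans no such summary. SAP 6.6 keeps unscheduled values out of summary statistics. It says they contribute to the assessment of clinical outliers, but SAP 17.3 defines no output for that.

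**The concern.** SI units put results on one unit scale, but they do not remove differences in method between laboratories. If baseline comes from one laboratory and Day 180 from another, the subject's change contains the method difference as well as any biological change. The table cannot separate the two, and nothing in the SAP marks which subjects are affected. Day 180 is the last look in the multiple-dose part of a first-in-human trial, and the quantity affected is a declared secondary endpoint.

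Cohorts enrol in sequence (Protocol 3.2), while placebo is pooled across dose levels (SAP 6.2). Each dose is therefore compared partly with placebo subjects from other calendar periods. If switching clusters in time, randomization within a cohort does not balance it between a dose group and pooled placebo. The resulting artefact could add to a real change or hide one.

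For liver tests, a raw value means a different degree of abnormality at laboratories with different ULNs, and the only by-dose display that uses the ranges stops at High.

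**Working it through.** The documents give no between-laboratory difference, switching rate, ULN or cohort date. All of these are assumptions below.

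**1. Sample size.** 4 + 4 + 8 + 8 + 12 + 12 + 12 = 60, which matches the stated figure. The multiple-dose part has 3 × 12 = 36 subjects: 9 on each dose and 3 × 3 = 9 on placebo. Single-dose subjects have no Day 180 visit, so the Day 180 placebo column holds at most 9.

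**2. One subject.** Let y0 be the true baseline value and y1 the true later value.
- Same laboratory: a constant offset c cancels in the change, (y1 + c) − (y0 + c). A proportional factor k cancels in the percent change, k·y1/(k·y0) − 1. Days 8, 29 and 90 and the single-dose Day 8 are in this position.
- Different laboratory at Day 180, with proportional difference d: reported percent change = 100 × [(1 + d)·y1/y0 − 1]. With no true change this equals 100d.

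**3. Group means.** If a share s of a group switches, its mean percent change moves by about d × s. The false difference from placebo is d × (s_dose − s_placebo).

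| Switching pattern | s_dose | s_placebo | Factor | d = 5% | d = 10% | d = 20% |
|---|---|---|---|---|---|---|
| Equal in dose group and placebo | s | s | 0 | 0 | 0 | 0 |
| Half of last cohort only (on average) | 0.5 | 1.5/9 | 0.333 | 1.7 | 3.3 | 6.7 |
| All of last cohort only | 9/9 | 3/9 | 0.667 | 3.3 | 6.7 | 13.3 |

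The last three columns are percentage points. Equal switching leaves no false difference, but each group's own change from baseline is still off by d × s.

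**4. Chance imbalance.** Suppose subjects switch independently with probability p, in two groups of 9. The probability that the groups differ by 3 or more switchers is 0.17 for p = 0.25 and 0.24 for p = 0.5. A gap of 3 gives a factor of 3/9 = 0.333, the middle row of the table.

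**5. Calendar.** A nominal Day 180 on 02 April 2020 implies Day 1 on 06 October 2019 (179 days earlier), or about 06 September 2019 with the +30-day window. Only subjects first dosed from about then could use the permission. Whether that date divides the cohorts cannot be told.

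**6. Grading of High.** With assumed ALT ULNs of 35, 45 and 55 U/L:
- ALT of 60 is 60/35 = 1.71, 60/45 = 1.33 or 60/55 = 1.09 × ULN.
- ALT of 110 is 110/35 = 3.14, 110/45 = 2.44 or 110/55 = 2.00 × ULN.

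All six fall in the same High cell.

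**7. Visits in the shift table.** The last injection is on Day 22, and Day 180 comes 180 − 22 = 158 days later. Whether that counts as on-treatment is not stated.

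**The case against.** The other side has a good deal of ground.

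- **The ranges are used.** A reader might infer that liver results are never put on a common scale. The documents do not support that. SAP 17.3.1 compares each result with the relevant laboratory's range, and SAP 17.3 builds a shift table on it. The out-of-range listing carries no on-treatment limit, so a raised Day 180 ALT would appear there. The scale is coarse, not absent.
- **Undefined does not mean excluded.** Single-dose subjects have one injection and one scheduled post-dose laboratory visit, Day 8. A strict dosing-period reading would leave them no shift table. Post-baseline is a natural reading, but the text does not settle it.
- **A drug effect is not implied.** A reader might infer that switches will gather in the highest dose and look dose related. No document gives cohort dates or switching counts. Placebo subjects have the same permission, and equal switching gives a false difference of 0. Day 180 is also far from dosing, and SAP 15.1 expects no quantifiable parent drug in plasma after 4 hours.
- **Liver injury is handled case by case**, through extra tests, Medical Monitor discussion and SAE reporting. The DSMB reviews laboratory values at escalation, and SAP 17.1.3 plans a table of TEAEs of CTCAE grade 3 or above. Nothing says that group means are read against a liver threshold.
- **Excluding switched results would do harm.** If the whole last cohort switched, that dose would have 0 of 9 values at Day 180, and SAP 6.1 prints N/A below n = 2.

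These points narrow the concern and shape the fix. They do not supply a rule for a changed laboratory or a by-dose view of how far liver results rose. The table shells named in SAP section 8 are not in the text available, so they may already carry a laboratory identifier. That would help with flagging but would not change the summaries described in SAP 17.3.

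**Conclusion.** The point holds, at modest weight. As written, SAP 17.3 puts any between-laboratory difference into the Day 180 change for each multiple-dose subject who switches. At most 36 subjects at one visit are exposed, and the number who switched is not given. Distortion of the comparison with placebo also needs unequal switching, which is possible but not shown. Under an assumed 5–20% method difference it ranges from 0 to 3.3–13.3 percentage points, and the upper figures require that only the last cohort switches, and all of it.

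Change from baseline is largely unaffected at Days 8, 29 and 90 and in the single-dose part. Safety analysis is descriptive, and the primary endpoint (TEAEs) is not touched. The separate liver point is a matter of resolution: the range-based displays exist but do not grade above High, and whether the shift table reaches Day 180 is unclear.

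**What to change.** Amend SAP 17.3 in three places:

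1. **Day 180 change.** Keep the full summary. Flag results from a laboratory other than the baseline laboratory. Beside it, add change and percent change restricted to subjects whose baseline and Day 180 come from the same laboratory, with n shown.
2. **Shift table.** Replace the undefined on-treatment limit with a statement that the table covers all scheduled post-baseline visits, including Day 180.
3. **Liver tests.** For ALT, AST, ALP and total bilirubin, divide each result by the reporting laboratory's ULN. Tabulate each subject's maximum post-dose multiple, from scheduled and unscheduled samples, by dose and placebo. Show ALT or AST together with total bilirubin.

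Cost: a laboratory identifier in the analysis dataset and a few extra outputs, using reference ranges that the plan already lists. No samples or visits are added. The same-laboratory summary may rest on a small n, or print N/A, if many subjects switch, which is why the full summary stays. These changes concern tabulation only; no clinical threshold or management rule is proposed.
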